1.4 BENEFIT - RISK ASSESSMENT

1.4.1 Benefits

Preclinical profiles of BI 655130 and clinical data from healthy volunteer trials suggest that BI 655130 is safe, tolerable and may address an unmet medical need in GPP patients. Data from the completed PoC trial 1368.11 demonstrate that BI 655130 treatment rapidly reduces the flare severity and clears pustules, the primary lesion in GPP, a disease closely linked to loss of function mutations in the natural IL36R antagonist. Please refer to IB for additional details ([c03320877](#)).

No relevant animal species is available for toxicology testing of the highly human specific antibody BI 655130. However, preclinical toxicology studies with a mouse surrogate antibody have demonstrated the safety of IL-36R inhibition in mice ([c03320877](#)).

A total of an estimated 378 subjects have been exposed to single or multiple i.v. doses of BI 655130 as of September 2019. For additional details please refer to IB ([c03320877](#)). BI 655130 was safe and well tolerated in four healthy volunteers trials evaluating the i.v. and s.c. formulation.

1.4.2 Risks

There are no identified or potential risks for BI 655130, based on the toxicology program or any clinical trials conducted for this product to date (see also [Section 1.2](#)). No other IL-36 receptor antagonist is currently approved, providing information on identified risks in molecules of this class.

The risks shown in the table below are hypothetical in nature; these are derived from general safety considerations of immunomodulatory drugs.

In order to protect the patient’s safety during conduct of this trial, an independent Data Monitoring Committee has been established for the periodic review of clinical trial safety data.

Table 1.4.2: 1 Risks

Hypothetical risks of clinical relevance for this trial	Summary of data, rationale for the risk	Mitigation strategy
Investigational Medicinal Product		
Drug-induced liver injury (DILI)	Rare but severe event, thus under constant surveillance by sponsors and regulators.	Timely detection, evaluation, and follow-up of laboratory alterations in selected liver laboratory parameters to ensure patients’ safety. See also Section 5.2.6 , adverse events of special interest”
Systemic hypersensitivity reaction	After administration of any biologic agent or protein, there is a possibility of occurrence of adverse immune reactions which can be systemic (e.g. anaphylactic reactions) or local (e.g. redness, pruritus, and or swelling at the injection site).	Patients with a history of allergy/hypersensitivity to the systemically administered trial medication agent or its excipients are excluded from the trial. In case of systemic hypersensitivity reactions including anaphylactic reaction emerging during or after administration of trial medication, the investigator should consider in accordance with severity of the reaction and local standard of care to interrupt and treat the condition. Systemic hypersensitivity reaction is defined as AESI. It is subject to close monitoring and investigators are requested to assess these conditions using the criteria discussed in the statement paper from Sampson HA [R11-4890].

Table 1.4.2: 1 Risks (cont.)

Hypothetical risks of clinical relevance for this trial	Summary of data, rationale for the risk	Mitigation strategy
Infections	
Inhibition of the immune response with an immune-modulating biologic may increase the risk of infections.
 
A recent characterisation of individuals with homozygous IL36R KO mutations revealed that normal immune function was broadly preserved suggesting that IL36 signalling pathway inhibition does not compromise host defenses [R17-3632].
	
Screening procedures for infections will be established for this trial. Patients with any relevant chronic or acute infections including human immunodeficiency virus (HIV), viral hepatitis or tuberculosis are excluded from the trial.
 
Treatment of infections should be initiated promptly according to standards of care.
 
Severe infections and opportunistic infections are considered AESI for this trial. These conditions and serious infections are subject to close monitoring.

Malignancies	
Inhibition of the immune response with an immune-modulating biologic may increase the risk of a decreased immune defence against malignancies.
 
A recent characterisation of individuals with homozygous IL36R KO mutations revealed that normal immune function was broadly preserved suggesting that IL36 signalling pathway inhibition does not compromise host defences [R17-3632].
	
Patients with a recent history of malignancy within 5 years will be excluded from participation in this trial.
 
In case of occurrence of malignant neoplasm other than appropriately treated basal cell carcinoma or squamous cell carcinoma of the skin or in situ carcinoma of uterine cervix, the investigator should discontinue treatment with BI 655130.
 
Diagnostics and treatment have to be initiated according to local standard of care.
 
Malignancies represent always serious adverse events and are subject to close monitoring.

Peripheral Neuropathy	
Three cases reported by the investigator as Guillain-Barré
	
Timely detection, evaluation, and follow-up of suspected

Hypothetical risks of clinical relevance for this trial	Summary of data, rationale for the risk	Mitigation strategy
	
syndrome (GBS) were received in ongoing clinical trials with spesolimab. A panel of independent neurologists and experts in the study of neuropathies assessed the 3 cases. Only 1 met level 4 diagnostic certainty for the diagnosis of GBS (lowest level on Brighton scale of 1 to 4). In that case, there was a coincident infection with SARS-CoV-2. The other 2 cases were assessed as not GBS. Observed cases showed a heterogenous pattern. A causal association to spesolimab to any of the reported cases was assessed to be unlikely.
 
As per assessment by the panel of external neurologists the nonspecific symptoms and findings in all three cases may best be referred to as peripheral neuropathy.
	
peripheral neuropathies to ensure patients' safety.
 
Targeted Follow up questions to gather detailed information in case of any event during trial to ensure proper decision making.
 
Trial treatment discontinuation criteria as well as criteria for trial treatment restart are implemented for relevant cases.

Table 1.4.2: 1 Risks (cont.)

Hypothetical risks of clinical relevance for this trial	Summary of data, rationale for the risk	Mitigation strategy
Trial procedures		
Blood Sampling	As with all blood sampling, there is a risk of mild pain, local irritation, or bruising (a black or blue mark) at the puncture site. Furthermore, there is a small	These risks will be addressed by careful safety monitoring and risk mitigation measures such as (a) close clinical monitoring for

Hypothetical risks of clinical relevance for this trial	Summary of data, rationale for the risk	Mitigation strategy
	risk of light-headedness and/or fainting. In rare cases, the puncture site can also become infected or nerves may be damaged, inducing long-lasting abnormal sensations (paresthesia), impaired sensation of touch and persistent pain.	AEs; (b) selection of experienced sites and site staff; (c) training.
Skin Biopsy	Can cause local bruising, inflammation, nerve damage and pain.	These risks will be addressed by careful monitoring and risk mitigation measures such as (a) close clinical monitoring for AEs; (b) selection of sites with experienced site staff; (c) training.
Other risks		
Withdrawal of Standard of Care and Administration of Placebo/ BI 655130	If the standard therapy is withdrawn and the patient is randomized to receive a placebo/BI 655130, the patient's condition could get worse during the course of the trial.	In the event of a GPP flare, the option of rescue treatment with open label BI 655130 is available for patients on placebo. Also, in an event of disease worsening, treatment with standard of care is always an option per physician discretion for all randomized patients

Based on the findings in the nonclinical studies conducted to date and in accordance with international regulatory guidelines, the inclusion of Women of Child Bearing Potential (WOCBP) in this study is justified. To minimize the risk of unintentional exposure of an embryo or foetus to the investigational drug, WOCBP must agree to the requirements for the pregnancy testing and contraceptive methods described in the protocol.

Benefit-Risk Assessment in context of COVID-19 pandemic for patients participating in clinical trials investigating Spesolimab:

A thorough assessment based on the data available as of 18 May 2020 has been conducted to evaluate whether spesolimab may pose a higher risk associated with COVID-19 infection. Additionally, the general risk of COVID-19 infection in context of the trial population's

underlying disease and common co-morbidities was assessed. The key aspects of the assessment are summarized below.

Spesolimab is an immune-modulating humanized monoclonal antibody that blocks the human IL-36 receptor and thereby the pro-inflammatory IL-36 pathway. Available non-clinical and clinical data in 378 subjects (see Investigators Brochure Version 7) have not shown an increased risk of infections with spesolimab. However, as reflected in [Table 1.4.2:1](#) above and the patient informed consent form, similar to other immune modulating biological treatments, spesolimab may hypothetically increase the risk of infections. Therefore, risk mitigation measures, such as exclusion of patients with increased risk of infections, close monitoring of adverse events, as well as guidance on treatment and handling of acute infections occurring during the trial have been included within this clinical trial protocol.

As any other acute infection, a suspected or diagnosed COVID-19 infection should be treated according to the standard of care and interruption of study medication should be considered.

Currently, information about the immune response in patients with COVID-19 is sparse and inconclusive. There are some reports suggesting high-levels of pro-inflammatory cytokines in the severe cases, with much of the morbidity associated with coronavirus infection, potentially related to immune activation and inflammation. To date, there is no reliable evidence suggesting a link between SARS-CoV-2 infections and the IL-36 pathway targeted by spesolimab. Considering the current knowledge of COVID-19 and the implemented risk mitigation measures addressing the potential risk of infections, patients studied in trials with spesolimab are not believed to be at higher risk of COVID-19 due to their background or concomitant diseases. Protocol-defined procedures do not impose undue risk to study participants.

The benefit-risk assessment of spesolimab remains favourable in the context of the COVID-19 pandemic. Patients participating in trials with spesolimab are expected to benefit from trial treatment and interruption of treatment may worsen their disease. Published guidance for the use of biologics during the COVID-19 pandemic recommends to continue treatment with biologics (e.g. NICE COVID-19 rapid guideline: severe asthma [\[R20-2257\]](#), American College of Allergy, Asthma&Immunology [\[R20-2258\]](#), and National Psoriasis Foundation [\[R20-2256\]](#)). In line with this guidance no systematic testing for SARS-CoV-2 is required to be performed on the trial. However, the investigator may choose to perform the testing as per his/her discretion if useful based on individual medical consideration and in the case of suspected COVID-19 infection. Patients may receive COVID-19 vaccination in line with local recommendations/guidance and approved labels. However, it is not known whether there is any negative impact of spesolimab on the protective effect of COVID-19 vaccines.

To address potential risks associated with operational aspects related to the participation in this clinical trial in context of COVID-19 pandemic, the following risk mitigation measures are to be considered based on local requirements and development of pandemic.

Every subject or patient will be assessed thoroughly, and individual benefit-risk assessments are made prior to study entrance and during the study by the investigator in respect of SARS-CoV-2 infection. As any other acute infection a suspected or diagnosed COVID-19 infection

should be treated according to the standard of care and interruption of study medication should be considered. In case of a confirmed infection, trial treatment will be discontinued immediately and appropriate measures for monitoring, treatment and quarantine will be implemented. The investigators will take the totality of information related to each single patient and the local COVID-19 situation into consideration when performing the individual benefit-risk assessment on a case-by-case basis. The patient may resume trial treatment following recovery from a SARS-CoV-2 infection if the patient is expected to derive clinical benefit, as agreed between the investigator and sponsor.

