3.3.4.1 Discontinuation of trial treatment

An individual patient will discontinue trial treatment if:

- The patient wants to discontinue trial treatment, without the need to justify the decision.
- The patient has repeatedly shown to be non-compliant with important trial procedures and, in the opinion of both, the investigator and sponsor representative, is not willing or able to adhere to the trial requirements in the future.
- The patient needs to take concomitant medication that interferes with the investigational medicinal product or other trial treatment.
- The patient can no longer receive trial treatment for medical reasons as per physician’s discretion (such as surgery, adverse events, other diseases, or pregnancy).
- If a hepatic injury alert (as defined in [Section 5.2.6.1.4](#)) is detected without identification of an alternative cause in the work-up according to the “DILI checklist”, the patient should not receive subsequent doses of trial medication.
- For individual stopping rules related to specific adverse events, please see [Section 4.2.1](#) “Other treatments and emergency procedures.”
- Worsening of clinical status or GPP symptoms requiring treatment with restricted medication ([Section 4.2.2.1](#)) in the investigator’s opinion.
- The patient experiences an infection with SARS-CoV-2 (as confirmed by PCR test). The patient may resume trial treatment following recovery from SARS-CoV-2 infection if the patient is expected to derive clinical benefit, as agreed between the investigator and sponsor.
- If peripheral neuropathy is suspected, treatment with spesolimab should be temporarily discontinued until a full neurological investigation has been conducted. After completion of the neurological investigation, treatment can be restarted based on medical judgement of the investigator.

If new efficacy/safety information becomes available, Boehringer Ingelheim will review the benefit-risk-assessment and, if needed, pause or discontinue the trial treatment for all patients or take any other appropriate action to guarantee the safety of the trial patients.

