4.2.1.1 Emergency procedures

Systemic hypersensitivity including infusion reactions and anaphylactic reaction

In case of systemic hypersensitivity including infusion reactions and anaphylactic reaction, emerging during or after infusion/injection of study medication, the investigator should consider in accordance with severity of the reaction and local standard of care to

- Immediately interrupt the infusion/injection
- Treat with systemic anti-histamines, i.v. steroids, and in case of a severe allergic reaction (e.g., anaphylactic reaction) epinephrine

Also draw a plasma sample for IgE and ADA and a serum sample for neutralizing antibody (Nab) as detailed in the Lab Manual (Central Laboratory). Consider also the evaluation of histamine, serum tryptase, and complement components.

In case of systemic hypersensitivity including infusion reactions, based on patient's clinical course and medical judgment, the infusion may be re-initiated in case of mild or moderate systemic hypersensitivity including infusion reactions (according to RCTC grading [R13-3515] in ISF) at lower speed with gradual increase to complete the infusion as detailed in the *Instructions for Preparation and Handling of BI 655130* in the ISF. Regardless, the total duration of infusion should not exceed 180 minutes (3 hours).

In case of anaphylactic reactions based on published criteria ([Appendix 10.1.6](#); [R11-4890](#)) that are suspected to be caused by the study medication, the investigator should discontinue treatment with BI 655130.

When a non-acute hypersensitivity reaction related to immune complexes (i.e., serum sickness) is suspected, draw a sample for the laboratory assessment for circulating immune complexes.

In case of potential systemic allergic reaction, blood samples for determination of serum tryptase will be collected 0.5 h, 2 h, 6 h, 24 h after onset of the event.

Severe infections (according to RCTC grading: refer to the ISF), serious infections, opportunistic or mycobacterium tuberculosis infections

Treatment of the infection should be initiated promptly according to local standard of care. No further study medication should be administered until the active infection has resolved. Treatment with BI 655130 may be restarted when the patient has recovered according to investigator's assessment.

Malignancies

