In case of occurrence of malignant neoplasm other than appropriately treated basal cell carcinoma or squamous cell carcinoma of the skin or in situ carcinoma of uterine cervix, treatment discontinuation is to be a consideration if deemed clinically appropriate by the investigator. In addition, diagnostics and treatment are to be initiated according to local standard of care.

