5.2.5 Other safety parameters

Local tolerability at the administration site of BI 655130 /placebo will be assessed by the investigator during the study drug administration visit (i.v. or s.c.) and at the time of AE assessment by questioning retrospectively since the last visit. Any observed local tolerability reaction, e.g. "swelling", "induration", "heat", "redness", "pain", and, "other findings" should be reported as adverse event.

Grade the intensity of the local tolerability according to RCTC grading (cf. ISF).

In case of an infusion reaction, monitor the patient per standard of care, grade the intensity of the reaction according to RCTC grading (cf. ISF) and proceed as described in [Section 4.2.1.1](#).

All cases of malignancies, sepsis or other serious infections and disseminated intravascular coagulation that are detected during the trial will be reported as SAEs. Please refer to the current list of “Always Serious AEs” provided in eDC.

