7.2.7 Interim analyses

To support a potential BI655130 acute flare treatment submission, an interim analysis of the clinical efficacy and safety data collected during the BI 655130 OL i.v rescue treatment and s.c. maintenance treatment periods for GPP flare may be performed. The interim data snapshot will include the data from the i.v. rescue treatment period and OL maintenance treatment period. The initial randomized s.c. treatments will remain blinded and these data will not be analysed as part of this interim analysis. The timing of the interim analysis is driven by the timing of the submission of the acute flare treatment. Further details on the specifications for this interim analysis will be presented in the trial statistical analysis plan.

In order to ensure the patient's safety during the trial, a fully external DMC, independent of the trial and project teams, will review all available un-blinded safety data as well as selected efficacy data at regular intervals following first-patient-in. A DMC SAP which describes the analyses required for assessment by the DMC will be produced. Further details will be provided in a DMC charter.

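### The protocol gives two different instructions on stopping BI 655130 after a new malignancy: Table 1.4.2:1 directs discontinuation, Section 4.2.1.1 leaves it to the investigator

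*Protocol*

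**What the plan says.** Protocol Section 1.4.2, Table 1.4.2:1, malignancies row. The mitigation column lists four measures:

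- patients with a malignancy in the previous 5 years are excluded;
- after a new malignant neoplasm outside the listed exceptions, treatment is stopped, in the words "or in situ carcinoma of uterine cervix, the investigator should discontinue treatment with BI 655130";
- diagnostics and treatment follow local standard of care;
- malignancies always count as serious adverse events and are closely monitored.

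Protocol Section 4.2.1.1, Malignancies. For the same occurrence, with the same exceptions, "treatment discontinuation is to be a consideration if deemed clinically appropriate by the investigator". Diagnostics and treatment again follow local standard of care.

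Protocol Section 3.3.4.1, on discontinuing trial treatment, has no malignancy rule of its own. One bullet begins "For individual stopping rules related to specific adverse events, please see" and points to Section 4.2.1. Another allows discontinuation for medical reasons at the physician's discretion. Neither mentions Table 1.4.2:1.

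**The concern.** Both sentences are current protocol text, and both tell the investigator what to do with study drug after the same serious event. The table is part of the benefit-risk assessment, and one of the measures it gives for this risk is an instruction to stop. The section to which sites are sent for stopping rules contains no such instruction, only a judgement to be made.

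An investigator inclined to continue would act within Section 4.2.1.1 and against the table. Two sites could therefore handle the same event differently, each with protocol text in support. It would also be unclear whether continued dosing is a protocol deviation, because Section 8 treats any departure from the protocol as one. What is at stake is patient safety and uniform conduct, not the trial's power or type I error.

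**Working it through.** No figure in the plan depends on this rule, so there is nothing to recompute. The check sets the texts side by side.

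1. **Trigger.** Both passages start from the occurrence of a malignant neoplasm. There is no difference in scope.

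2. **Exceptions.** Both exempt appropriately treated basal cell and squamous cell carcinoma of the skin and in situ carcinoma of the cervix. The lists match, so the differing instructions cannot be explained by different patient groups.

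3. **Instruction.** The table directs discontinuation and attaches no condition. Section 4.2.1.1 asks that discontinuation be considered and makes it depend on the investigator's view of clinical appropriateness.

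4. **Whether the wording difference carries meaning.** Section 4.2.1.1 itself uses the directive form elsewhere. For anaphylactic reactions "that are suspected to be caused by the study medication, the investigator should discontinue treatment with BI 655130". The closing words are those that the table uses for malignancy. Within one section, then, the protocol uses a directive for one event and a discretionary form for another. The malignancy sentence in that section cannot be read as a loose way of stating the directive.

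5. **Whether the cross-reference settles it.** Section 3.3.4.1 leads to Section 4.2.1 and so to the discretionary text. It does not name malignancy, does not cite the table and does not say which text prevails. The table's sentence remains in force as written.

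6. **Whether one text is superseded.** Both stand in the body of the protocol. The available part of the amendment log in Section 11 records no change to the malignancy wording. The end of the Global Amendment 3 entry was not available to check, but nothing logged there would remove the difference between the two current passages.

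7. **Where the texts diverge in practice.** An investigator who discontinues satisfies both. An investigator who judges continuation appropriate satisfies Section 4.2.1.1 but not the table. Only this second case is affected.

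8. **What limits the effect.** Under Protocol Section 5.2.5, "All cases of malignancies, sepsis or other serious infections and disseminated intravascular coagulation that are detected during the trial will be reported as SAEs". Under Section 7.2.7, an external DMC "will review all available un-blinded safety data as well as selected efficacy data at regular intervals". These events will therefore be seen, although neither provision tells an investigator which rule to follow.

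9. **Effect on the analysis.** Protocol Section 2.1.1 compares patients as randomized whether or not they stay on treatment. SAP Section 5.1 does not treat stopping study drug as an intercurrent event. Protocol Section 7.2.2 uses on- and off-treatment data up to Week 48. The choice of rule could change drug exposure in the few patients affected, but not how they enter the primary comparison.

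**The case against.** The strongest reply is that the operative rule can be found. Table 1.4.2:1 sits in the introduction and describes its risks as hypothetical. The section on discontinuing treatment sends sites to Section 4.2.1, where they meet the discretionary text. On this view the table is only a summary. It also fails to track Section 4.2.1.1 in other rows. The hypersensitivity row, which includes anaphylaxis, says only that "the investigator should consider in accordance with severity of the reaction and local standard of care to interrupt and treat the condition", while Section 4.2.1.1 has a stopping rule for suspected drug-caused anaphylaxis. The infections row gives no dosing rule, although Section 4.2.1.1 withholds drug until the infection resolves. It may be added that the directive is a recommendation to the investigator and not an absolute bar, and that discretion alone would already let sites differ.

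Much of this stands. The pointer does suggest where sites will look, and no weight is placed here on how the table's other rows are worded. But those rows leave detail out, whereas the malignancy row states an instruction that the operative section does not give. If Section 4.2.1.1 governs, the table misdescribes the mitigation; if the table governs, Section 4.2.1.1 does. Either way one passage needs correcting. Discretion may well be what the sponsor intends, but then the benefit-risk table should not say otherwise.

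A reader might infer that stopping treatment is the protocol's mitigation for malignancy and that Section 4.2.1.1 removes it. The documents do not support that: discontinuation is one of four measures in the row, and exclusion at entry, diagnostics and treatment, and SAE handling are not in dispute.

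**Conclusion.** The inconsistency is real but narrow. For the same event and the same exceptions, the protocol directs discontinuation in one place and leaves it to clinical judgement in another, with no stated precedence. It should be corrected because it concerns stopping treatment after a serious event. It matters where an investigator would judge continuation appropriate, and there it bears on patient safety and consistent site conduct.

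The size is not quantified: the documents give no malignancy rate from which to estimate how many patients could be affected. SAE reporting and DMC review limit the consequence.

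Two further readings are tempting and go beyond the documents. One is that the conflict biases the efficacy result; the treatment comparison is made regardless of discontinuation, so the effect on it is small. The other is that the pointer in Section 3.3.4.1 shows the table to be the passage in error; the pointer shows where stopping rules are kept but does not say that the table yields. The conclusion rests on reading both passages as current and on the directive form meaning in the table what it means for anaphylaxis in Section 4.2.1.1.

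**What to change.** Reconcile the malignancies row of Table 1.4.2:1 with the Malignancies paragraph of Section 4.2.1.1, so that a single rule, chosen by the sponsor's clinical team, is stated consistently in both. The pointer in Section 3.3.4.1 can stay. The peripheral neuropathy row, which says only that "Trial treatment discontinuation criteria as well as criteria for trial treatment restart are implemented for relevant cases", might look like a model for replacing the malignancy rule with a cross-reference. Pointing the row to Section 4.2.1.1 as it now reads would, however, select the discretionary rule by default, so the clinical decision has to come first.

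The cost is a wording change by protocol amendment and a notice to sites. Data collection, the SAP and the analysis do not change.
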